14.3. Analysis Populations

Safety Population:

All subjects who are administered any test article excluding subjects who drop out prior to administering any test article. At least one observation should be recorded.

Per-Protocol Population:

All subjects who successfully complete all visits and do not substantially deviate from the protocol (i.e. have major protocol deviations) as determined by the trial cohort review committee prior to database hard lock. Justification for the exclusion of subjects with major protocol deviations from the perprotocol population set will be documented in a memo to file.

Intent-to-Treat (ITT) Population:

All randomized subjects regardless of actual treatment and subsequent withdrawal from the study or deviation from the protocol. At least one observation should be recorded.

14.4. Level of Statistical Significance

All planned analysis for this study will be conducted with an overall Type I error rate of 5%. Unless otherwise specified, all statistical tests will be 2-sided.

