14.2. Sample Size Justification

This study was designed and powered to test for non-inferiority of the Test relative to the Control eye drops with respect to the overall ocular comfort score using Visual Analog Scale for Ocular Comfort (VAS), with a minimum power of 90% and two-sided Type I error rate of 0.05. A non-inferiority margin of -20 will be used to test the hypothesis. If the Test eye drops perform on average worse by more than 20 points on the VAS may be considered clinically unacceptable.

Historical data from a previous study, was utilized in assessing scenarios for power analysis of the VAS. Summary statistics from the historical study are presented in Table 8. The historical VAS, for the difference of 30 days follow-up from baseline scores, shows a slight left skew, indicating there is a possibility of a non-normally distributed result in this study. Hence, the sample size calculations were conducted using (i) two-sided, parametric two-sample t-test for normally distributed data, and (ii) non-parametric Wilcoxon Rank Sum test for non-normal data in PASS software Version 21.0.6 (2021) (NCSS LLC, Kaysville UT)¹¹.

Table 8: Summaries for Historical Overall Comfort Score Change from Baseline at 30-Day Follow-up using Visual Analog Scale (VAS) Questionnaire - Intent-To-Treat Population

Group	Number	Mean	Standard	Minimum	Median	Maximum
	Analyzed	Difference	Deviation			
Blink [®] Tears	80	12.5	25.74	-69	13.0	62.0
Investigational Lipid	75	20.3	23.24	-21	18.0	78.0
Drop						

Sample Size Calculation using Parametric Method

Table 9 displays the sample size estimates for the primary endpoint using a two-sample *t*-test for non-inferiority, for different scenarios of standard deviations and dropout rates.

Standard	Sample	Total	Sample size per	Total sample	Sample size per	Total sample
deviation	size	sample	arm including a	size including	arm including a	size including
	per	size	5% dropout rate	5% dropout	10% dropout	10% dropout
	arm			rate	rate	rate
25	34	68	36	72	38	76
30	49	98	52	104	55	110
35	66	132	70	140	74	148

 Table 9: Sample size calculations using two-sample t-test for non-inferiority

Note: Sample size relating to 90% power, Type I Error rate of 0.05, assumed effect size of 0, non-inferiority margin of -20.

Sample Size Calculation using Non-Parametric Method

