Table 10 displays the sample size estimates for the primary endpoint using Wilcoxon Rank Sum test for non-inferiority, for different scenarios of standard deviations and dropout rates.

Standard deviation	Sample size per	Total sample size	Sample size per arm including a 5% dropout	Total sample size including 5% dropout	Sample size per arm including a 10% dropout	Total sample size including 10% dropout
	arm		rate	rate	rate	rate
25	36	72	38	76	40	80
30	52	104	55	110	58	116
35	70	140	74	148	78	156

Table 10: Sample size calculations using Wilcoxon Rank Sum test for non-inferiority

Note: Sample size relating to 90% power, Type I Error rate of 0.025, assumed effect size of 0, non-inferiority margin of -20.

The recommended sample size is approximately 116 subjects which is determined to be sufficient to meet both normal and non-normally distributed options.

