 ε_{ij} = a random error associated with the jth subject in the ith investigational site.

Assume that δ_i and ϵ_{ij} are independent and identically distributed such that $\delta_i \sim N(0, \sigma_{site}^2)$; $\epsilon_{ii} \sim N(0, \sigma^2)$, and are independent of each other.

The non-inferiority test will be based on the least square mean change difference and corresponding 95% confidence interval from the final model. Non-inferiority will be concluded if the lower limit of the 95% confidence interval is above non-inferiority margin of -20.

Primary Analysis Plan B (Assuming-non-normal distribution)

The difference of VAS Ocular comfort scores between treatment group and control group in mean change from baseline at 30-Day follow-up (Test minus Control) and two-sided 95% confidence interval

will be computed using a bootstrap methodology¹³. A total of 4000 bootstrap iterations will be used following the suggestions of Samuelson and Petrick¹⁴. Bias-adjusted 95% confidence interval will also be calculated. The assessment of the impact of the autocorrelation for between subjects repeated measurements, is defined by the difference between the observed statistic compared to the bootstrapped population mean (bias = observed minus bootstrapped population mean). This approach was recommended for all estimations of statistical inference since it accommodates correlated data. The bootstrap analysis will be performed using SAS MACRO procedures as discussed by Davison, AC and Hinkley, DV^{12} .

The non-inferiority test will be based on mean change difference and corresponding 95% confidence interval using the 2.5th percentile and 97.5th percentile from the bootstrapping model. The lower bound of the 95% confidence interval will be compared to the non-inferiority margin of -20. If the lower bound is greater than or equal to -20, the null hypothesis will be rejected, and the Test will be considered non-inferior to Control.

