14.6. Secondary Analysis

Change in Overall Quality of Vision from Baseline at 30-Day Follow-Up Using VAS Scores

The overall change of quality of vision from baseline at 30-Day follow-up will be analyzed with the same hypotheses and models as primary analyses. If the Shapiro-Wilks test result is significant, then *Primary Analysis Plan B* will be adapted for overall change of quality of vision at 30-Day follow-up. Otherwise, *Primary Analysis Plan A* will be adapted for this secondary analysis.

Hypothesis Testing:

The two separate null and alternative hypotheses for non-inferiority of Test relative to Control are as follows:

$$H_0: \Delta \le -20 \\ H_A: \Delta > -20$$

where Δ is the difference between treatment group in mean change from baseline at 30-Day follow-up (Test minus Control).

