14.7. Other Exploratory Analysis

Exploratory analyses will only be conducted if all primary and secondary hypotheses are met. If conducted, exploratory analysis will be analyzed for the Safety population. The exploratory analyses will be analyzed as follows:

Change in Overall Ocular Comfort from Baseline at 14-Day Follow-Up Using VAS Scores The overall change in ocular comfort from baseline at 14-Day follow-up will be analyzed as described in primary analyses (section 14.5).

Change in Overall Quality of Vision from Baseline at 14-Day Follow-Up Using VAS Scores The overall change in ocular comfort from baseline at 14-Day follow-up will be analyzed as described in secondary analyses (section 14.5).

Corneal Staining (Grade 2 or higher) Using FDA Scale

Corneal staining response using FDA grading scale (i.e. Grade 0 = None, Grade 1 = Trace, Grade 2 = Mild, Grade 3 = Moderate and Grade 4 = Severe) will be monitored by surveillance tabulation by

treatment group. If the rates between groups are significantly different from each other, then further analyses will be performed.

Subject's reported ocular symptoms

Subjects are asked to report if they experienced any ocular symptoms at Baseline and during each follow-up. If the number of reported ocular symptoms exceeds 5% total population, further analyses will be done to investigate the correlation of ocular symptoms to the Test drops.

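### Comfort and vision are each tested for non-inferiority at one-sided 2.5% with no stated order, so vision can be claimed after comfort fails and the pair is not held at the level used for sizing

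*Combined protocol and SAP*

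**What the plan says.** Section 2.3 states two formal non-inferiority hypotheses, each with a margin of -20 points: comfort as primary and quality of vision as secondary.

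- **Level.** Section 14.4: "All planned analysis for this study will be conducted with an overall Type I error rate of 5" per cent, followed by "Unless otherwise specified, all statistical tests will be 2-sided".
- **Sizing.** Section 14.2 sizes the trial on comfort "with a minimum power of 90% and two-sided Type I error rate of 0.05". The note to Table 10 reads "Note: Sample size relating to 90% power, Type I Error rate of 0.025, assumed effect size of 0, non-inferiority margin of -20".
- **Comfort decision.** Section 14.5, Plan A: "Non-inferiority will be concluded if the lower limit of the 95% confidence interval is above non-inferiority margin of -20". Plan B applies the bootstrap 95% interval: "If the lower bound is greater than or equal to -20, the null hypothesis will be rejected".
- **Vision decision.** Section 14.6: the secondary endpoint "will be analyzed with the same hypotheses and models as primary analyses".
- **The only stated precondition.** Section 14.7: "Exploratory analyses will only be conducted if all primary and secondary hypotheses are met".

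No section makes the vision test depend on the comfort result, divides the error rate between them, or names a multiplicity procedure. Section 14.9 defers only the imputation details to a SAP, and Section 14.10 says that the analysis will follow the sections above it.

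**The concern.** The plan sets an overall error rate and then makes two formal claims, each with the full 95% interval. Section 14.7 places a condition in front of the exploratory analyses, but no such condition stands between primary and secondary. Calling one endpoint primary and the other secondary ranks them. It does not say what may be concluded about vision once comfort has failed.

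Two things are at stake. First, the joint error rate of the two claims is not held at the one-sided 2.5% to which the trial was sized. Secondly, a trial that misses its primary objective could still report non-inferiority for vision, with no rule agreed beforehand on how that result should be read. The synopsis calls the study confirmatory, and Section 2.1 says it supports product registration in the European Union, so the status of each claim should be settled before the data are seen.

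**Working it through.** **Inputs.** Margin -20, assumed true difference 0, power 90%, SD 25, 30 or 35, and 10% dropout (Section 14.2, Tables 9 and 10). 1:1 allocation (Section 5.1). Decision by the lower limit of a two-sided 95% interval (Sections 14.5 and 14.6). The correlation between the comfort and vision test statistics is not in the documents, so I take 0 to 0.9 as an assumed range.

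**Step 1. What level does the plan work at?** For a two-sample t-test, find the smallest n per arm for which a noncentral t variable with 2n - 2 degrees of freedom and noncentrality 20 / (SD × √(2/n)) exceeds the critical value with probability at least 0.90.

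| Per arm | SD 25 | SD 30 | SD 35 |
|---|---|---|---|
| Table 9 | 34 | 49 | 66 |
| Recomputed, one-sided 0.025 | 34 | 49 | 66 |
| Recomputed, one-sided 0.05 | 28 | 40 | 54 |

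Multiplying the one-sided 0.025 sizes by π/3 and rounding up gives 36, 52 and 70, which is Table 10. At SD 30, 52 / 0.90 = 57.8, so 58 per arm and 116 in total. The tables therefore reproduce at one-sided 0.025 and not at one-sided 0.05. The working standard is one-sided 2.5% per claim, which is the two-sided 5% of Section 14.2.

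**Step 2. Joint error as written.** Put both true differences at -20 and treat the two statistics as bivariate normal (a large-sample approximation):

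P(at least one false claim) = 0.025 + 0.025 - P(both false claims)

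P(false vision claim, comfort not shown) = P(at least one) - 0.025

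At correlation 0, P(both) = 0.025² = 0.000625, so the first quantity is 0.05 - 0.000625 = 0.0494.

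| Assumed correlation | At least one false claim | Ratio to 2.5% | False vision claim, comfort not shown |
|---|---|---|---|
| 0 | 4.94% | 1.98 | 2.44% |
| 0.5 | 4.54% | 1.82 | 2.04% |
| 0.7 | 4.17% | 1.67 | 1.67% |
| 0.9 | 3.52% | 1.41 | 1.02% |

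The ceiling at any correlation is 0.025 + 0.025 = 5%.

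**Step 3. How readily can vision stand alone?** Suppose comfort is truly at the margin and vision is truly equal, with an assumed SD of 30 for vision and 52 per arm. The noncentrality for vision is 20 / (30 × √(2/52)) = 3.40, so vision passes with probability Φ(3.40 - 1.96), about 0.925. With independent statistics, comfort fails and vision passes with probability 0.975 × 0.925 = 0.90. The result is also 0.90 at correlations 0.5 and 0.7. In this scenario the vision result is correct, so it is not a Type I error. It shows that a lone vision result is a realistic outcome for which the plan has no rule.

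**Step 4. Joint error with a fixed order.** If comfort is truly at or below the margin, any false claim first requires comfort to pass, which has probability at most 2.5%. If comfort is truly non-inferior, only the vision claim can be false, again with probability at most 2.5%. The joint error is therefore at most 2.5% at every correlation.

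**The case against.** The strongest reply is that Section 14.4 is kept. Two one-sided 2.5% tests cannot together exceed 5%. The alternative hypotheses are written one-sided, Section 14.4 allows for exceptions to two-sided testing, and the Table 10 note gives 0.025. This stands: a reader might infer that the plan breaks its own overall rate, and taken literally it does not. What remains is that Section 14.2 sizes the trial at two-sided 5%, and the pair is not held at that level.

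A reader might also infer that the false-claim rate is nearly doubled. The documents do not support that as a general statement. It applies only near independence, with both true differences exactly at the margin. The two scores come from the same subjects at the same visits, so positive correlation is plausible, and at 0.9 the ratio is 1.41.

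Thirdly, comfort alone is primary and alone drives the sample size, so its error stays at one-sided 2.5% whatever happens to vision. No section says that success may rest on vision. This also stands, and it confines the point to vision used as a confirmatory claim. The formal hypothesis and margin in Section 2.3 leave that use open.

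Finally, error control does not by itself forbid a secondary claim after a failed primary: splitting the error rate would control it and still allow that claim. This is correct. Requiring comfort first is a choice of hierarchy. It fits the plan's own ranking and costs less than a split.

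A testing order might appear in a separate SAP. Nothing in the documents says so.

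**Conclusion.** The point holds in a limited form. The plan does not say whether vision may be claimed when comfort fails, and it does not hold the two claims jointly at one-sided 2.5%. With both true differences at -20, the chance of at least one false claim is up to 4.9%, falling to 3.5% at a correlation of 0.9, against at most 2.5% with a fixed order. These figures rest on the assumed correlation and on both endpoints lying exactly at the margin.

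The comfort conclusion, its error rate and the sample size are not in question. The omission is worth correcting because it changes what may be concluded about vision and is almost free to repair.

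**What to change.** Add to Sections 14.4 and 14.6:

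> The two non-inferiority hypotheses are tested in fixed order, comfort and then quality of vision, each by its two-sided 95% confidence interval. Non-inferiority for vision is claimed only if non-inferiority for comfort has been shown. Both intervals are reported in either case. The familywise level for the two claims is one-sided 2.5%.

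The sample size stays at 116 and the power for comfort is unchanged. The downside is small: vision cannot be claimed as confirmatory if comfort fails, although its interval is still reported.

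The alternative, one-sided 1.25% for each claim, is dearer. At SD 30 and 90% power the t-test needs 58 per arm. Then 58 × π/3 = 60.7, so 61 per arm, and 61 / 0.90 = 67.8, so 68 per arm or 136 in total. Keeping 52 completers per arm would leave each test with about 85% (Wilcoxon) to 87% (t-test) power.

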14.5. Primary Analysis

All primary and secondary analyses will be conducted on intend-to-treat (ITT) population. Because the hypotheses are testing the non-inferiority of the Test related to the Control, a sensitivity analysis for the primary and secondary hypotheses will be performed on the per-protocol (PP) population to assess the robustness the results.

Ocular Comfort (VAS) Score: Ocular Comfort scores are recorded using Visual Analogue Scale of 0 to 100.

Primary Hypotheses for Plan A or Plan B:

The null and alternative hypotheses for non-inferiority of Test relative to Control are as follows:

$$\begin{array}{l} H_0: \Delta \leq -20 \\ H_A: \Delta > -20 \end{array}$$

where Δ is the difference in mean change from baseline at 30-Day follow-up between treatment group and control group (Test minus Control).

The Ocular Comfort Scores will be analyzed for normality using the Shapiro-Wilk test. If the data is normally distributed, then Primary Analysis Plan A will be implemented. Otherwise, Primary Analysis Plan B will be implemented.

Primary Analysis Plan A (Assuming Normality)

The overall change of ocular comfort score from baseline at 30-Day follow-up will be analyzed using a linear mixed model. The subjects are the level one units, and the investigational sites are the level two units. The model will include treatment group (Test, Control) as a fixed effect, and investigational site as a random effect. Age and gender will be included in the model as covariates. The log-likelihood ratio test may be used to assess the homogeneity of the variances with respect to treatment and sites. The Kenward and Roger¹² method will be used to calculate the denominator degree of freedom.

The model for each hypothesis is:

Let y_{ij} denote the change in VAS ocular comfort score from baseline at 30-Day follow-up for the j^{th} subject from the i^{th} site (j = 1, ..., n; i = 1, 2, ..., 8). The linear mixed model will be constructed as follows:

 $y_{ii} = \beta_0 + \beta_1 \cdot BASE_{ii} + \beta_2 \cdot TRT_{ii} + \beta_3 \cdot Age_{ii} + \beta_4 \cdot Gender_{ii} + \delta_i + \epsilon_{ii},$ where

- β₀ = Intercept
 BASE_{ij} = VAS ocular comfort score at baseline for the jth subject in the ith investigational
- TRT_{ij} = treatment assigned to the j^{th} subject in the i^{th} investigational site (Test vs Control eye drop group)
- β_2 = the treatment effect of interest
- δ_i = a random effect (subject-specific intercept) term for the ith site
 ε_{ij} = a random error associated with the jth subject in the ith investigational site.

Assume that δ_i and ϵ_{ij} are independent and identically distributed such that $\delta_i \sim N(0, \sigma_{site}^2)$; $\epsilon_{ii} \sim N(0, \sigma^2)$, and are independent of each other.

The non-inferiority test will be based on the least square mean change difference and corresponding 95% confidence interval from the final model. Non-inferiority will be concluded if the lower limit of the 95% confidence interval is above non-inferiority margin of -20.

Primary Analysis Plan B (Assuming-non-normal distribution)

The difference of VAS Ocular comfort scores between treatment group and control group in mean change from baseline at 30-Day follow-up (Test minus Control) and two-sided 95% confidence interval

will be computed using a bootstrap methodology¹³. A total of 4000 bootstrap iterations will be used following the suggestions of Samuelson and Petrick¹⁴. Bias-adjusted 95% confidence interval will also be calculated. The assessment of the impact of the autocorrelation for between subjects repeated measurements, is defined by the difference between the observed statistic compared to the bootstrapped population mean (bias = observed minus bootstrapped population mean). This approach was recommended for all estimations of statistical inference since it accommodates correlated data. The bootstrap analysis will be performed using SAS MACRO procedures as discussed by Davison, AC and Hinkley, DV^{12} .

The non-inferiority test will be based on mean change difference and corresponding 95% confidence interval using the 2.5th percentile and 97.5th percentile from the bootstrapping model. The lower bound of the 95% confidence interval will be compared to the non-inferiority margin of -20. If the lower bound is greater than or equal to -20, the null hypothesis will be rejected, and the Test will be considered non-inferior to Control.

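### A normality test decides whether the primary analysis adjusts for baseline and site; the adjusted model should be used whatever the result

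*Combined protocol and SAP*

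**What the plan says.** Section 14.5 opens the primary analysis with a gate: "The Ocular Comfort Scores will be analyzed for normality using the Shapiro-Wilk test". It continues: "If the data is normally distributed, then Primary Analysis Plan A will be implemented. Otherwise, Primary Analysis Plan B will be implemented".

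- **Plan A** is a linear mixed model for change in VAS comfort at Day 30. It has treatment, age and gender, a random site effect and, in the model equation, baseline VAS. Its errors are assumed normal.
- **Plan B** computes "The difference of VAS Ocular comfort scores between treatment group and control group in mean change from baseline at 30-Day follow-up (Test minus Control"), with a percentile interval from 4000 bootstrap iterations. No baseline, age, gender or site term is stated, and no resampling unit.

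Both plans use the same Δ and the same margin of -20. Their decision rules are worded differently. Plan A: "Non-inferiority will be concluded if the lower limit of the 95% confidence interval is above non-inferiority margin of -20". Plan B: "If the lower bound is greater than or equal to -20, the null hypothesis will be rejected".

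Section 14.6 carries the gate over to the secondary endpoint: "If the Shapiro-Wilks test result is significant", Plan B is used for quality of vision, otherwise Plan A.

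Section 5.1 stratifies randomization by site. Section 14.9 leaves only the imputation methods to a SAP, and section 14.10 says the analysis follows the preceding sections.

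**The concern.** The rule is written in advance, but the estimator it selects depends on the outcome data, and the two estimators differ in more than their distributional assumption. A non-normal outcome is no reason to drop the baseline score or the randomization stratum, yet Plan B as written drops both.

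The trigger is also unclear. Section 14.5 names comfort scores without saying whether these are Day-30 scores, changes, scores within arm or residuals, and gives no level for the test. Section 14.2 describes skew in the change ("The historical VAS, for the difference of 30 days follow-up from baseline scores, shows a slight left skew") and section 14.6 speaks of a plan that "will be adapted for overall change of quality of vision at 30-Day follow-up", so change scores are the more natural reading. Plan A, however, assumes normal errors, so a test on scores of either kind does not check its assumption.

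At stake is the width of the primary interval, and whether two competent programmers would report the same primary result.

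**Working it through.** **1. The plan's own figures reproduce.** A non-inferiority t-test (noncentral t, one-sided 0.025, margin 20, true difference 0, SD 30) needs 49 per arm, as in Table 9. Dividing by the Wilcoxon efficiency 3/π gives 51.3, so 52, as in Table 10. Then 52/0.90 = 57.8, so 58 per arm and 116 in total. At 52 per arm the unadjusted mean-difference test has 92.0% power at SD 30 and 97.5% at SD 25.74. The sample size is not in question.

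**2. Width of the unadjusted interval.** With SD 25.74 (Blink Tears, Table 8) and 52 per arm, the half-width is 1.983 × 25.74 × √(2/52) = 10.01 points.

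**3. Gain from baseline adjustment.** Let ρ be the baseline to Day-30 correlation and k the baseline SD divided by the Day-30 SD. The documents give neither, so both are assumed. The ratio of unadjusted to adjusted width is √[(k² + 1 − 2ρk)/(1 − ρ²)]. For k = 1 and ρ = 0.5 this is √(1/0.75) = 1.155.

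| k | ρ = 0.3 | ρ = 0.5 | ρ = 0.7 |
|---|---|---|---|
| 0.8 | 1.129 | 1.058 | 1.010 |
| 1 | 1.240 | 1.155 | 1.085 |
| 1.25 | 1.411 | 1.323 | 1.262 |

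The ratio is never below 1, and equals 1 only when the slope of Day 30 on baseline is 1 (ρ = k). At k = 1 the adjusted half-widths are 8.07, 8.67 and 9.23 points. The matching power at SD 30 is 98.7%, 97.3% and 95.5%.

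**4. How often Plan B would run.** Assume a 0.05 level and n = 104. With skew-normal change scores, Shapiro-Wilk rejects in 5%, 7%, 15% and 46% of trials at absolute skewness 0, 0.1, 0.25 and 0.5. Table 8 does not settle the skew: mean minus median is 12.5 − 13.0 = −0.5 for Blink Tears and 20.3 − 18.0 = +2.3 for the lipid drop.

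The whole two-stage procedure was then simulated:
- 8 sites of 13, assumed site SD 5, mean change +12.5, equal visit SDs, scores clipped to 0-100, arms pooled for the normality test.
- Plan A fitted by REML with 92 df in place of Kenward-Roger; Plan B as a within-arm percentile bootstrap with 600 draws.
- 2000 trials per setting at difference 0, and 3000 at the null.

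Plan B rates at SD 25.74 (before clipping), for ρ = 0.3 / 0.5 / 0.7:

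| Assumed baseline mean | Change tested | Raw Day-30 tested |
|---|---|---|
| 40 | 4.4 / 4.7 / 8.7% | 4.8 / 29.5 / 97.9% |
| 50 | 5.0 / 4.5 / 9.9% | 33.9 / 77.8 / 99.9% |
| 60 | 4.5 / 5.5 / 16.6% | 96.7 / 99.8 / 100% |

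In these nine settings the Plan B interval averaged 4-23% wider than Plan A's.

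**5. Effect on the decision.** Compared with Plan A throughout, the switch costs at most 0.1 points of power (change tested) or 1.3 points (raw tested) at SD 25.74. At SD 30 it costs at most 0.3 or 3.2 points, the worst case being 99.4% to 96.2%. One-sided type I error over all 18 settings is 1.9-3.5% with the switch and 1.9-3.2% for Plan A alone.

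**6. Sensitivity to the tested variable.** A separate simulation at change SD 30, with site as fixed effects, compared testing change scores with testing residuals. Under moderate left skew the two selected different plans in about 22-56% of trials. The Plan A and Plan B point estimates differed by about 2-3 points on average.

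**The case against.** The strongest reply is that the effect is small. The rule is prespecified, both plans target the same Δ and margin, and a wider unadjusted interval is valid and, for non-inferiority, conservative. The sample size was planned on an unadjusted comparison. On the natural change-score reading, Plan B is rare where it costs most. Multiplying the highest rate by the equal-SD widening gives 5.0% × 24% = 1.2% at ρ = 0.3, 5.5% × 15.5% = 0.9% at ρ = 0.5 and 16.6% × 8.5% = 1.4% at ρ = 0.7. The average loss over trials is thus about 0.1 VAS points of half-width. The high Plan B rates all come from the less natural raw-score reading, and the correlation, visit SDs, baseline mean and site SD are all assumed. This stands, and it limits the point to precision and clarity.

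Two further replies carry less weight. Section 14.1 calls itself a general description, so a SAP outside these documents might complete Plan B. However, section 14.9 defers only imputation and section 14.10 binds the analysis to the text as it is.

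It may also be said that naming the tested variable and bootstrapping the adjusted coefficient in Plan B would suffice. That would recover most of the precision, but would keep a data-driven switch that no longer serves a purpose.

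**Conclusion.** The concern holds. As written, a normality test on an unclearly identified variable decides whether the primary and secondary estimates are adjusted for baseline, age, gender and site. When Plan B runs, its interval is expected to be wider than the collected data allow unless the Day-30-on-baseline slope is 1. With equal visit SDs the widening is 8-24% over assumed correlations of 0.7 down to 0.3. Over the assumed SD ratios of 0.8 to 1.25 it ranges from 1% to 41%.

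The direction does not depend on these assumptions; the size does. How often Plan B runs depends mainly on the reading: 4-17% of simulated trials at SD 25.74 if changes are tested, 5-100% if raw Day-30 scores are. The unequal wording of the two decision rules at exactly -20, a value that belongs to H0, has negligible numerical effect.

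The change is worth making because it improves the primary estimate at almost no cost.

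**What to change.** - Delete the Shapiro-Wilk gate in sections 14.5 and 14.6. Make the Plan A model (baseline, treatment, age, gender, random site) the single primary analysis whatever the normality result, and name baseline in the prose as well as the equation. Use the same model for quality of vision with its own baseline.
- State one rule: non-inferior only if the lower 95% limit is strictly greater than -20.
- If robustness to non-normality is wanted, report a robust-variance interval or a bootstrap of the adjusted treatment coefficient as a sensitivity analysis. State the resampling unit, and avoid resampling within the site-by-arm cells, planned at 6-8 subjects in Table 1. In a simulation (assumed site SD 5, ρ = 0.5, site as fixed effects, 400 draws), coverage was 91.7% resampling within site and arm, and 94.0% within arm.
- Optionally, note in section 14.2 that 52 per arm comes from a Wilcoxon test that neither plan performs, and that the unadjusted mean comparison at SD 30 has 92% power with that number.

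The cost is a short wording amendment, sent to the IEC/IRB where appropriate (section 18.3 lists protocol revisions). Baseline VAS, age, gender and site are already collected, and a sensitivity interval takes about the same programming as Plan B.
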